8.0 Protection of Human Subjects

Prior to implementation of this study, the protocol will be approved by the WFU Institutional Review Board (IRB). All subjects will provide written informed consent prior to enrollment in the study.

9.0 Data Submission Schedule

Appendix A – Eligibility Checklist and Registration Form:

- Submitted to Registrar at the time of registration

Appendix B – Demographics, Social and Medical History, Baseline Lab Data Collection Form: - completed at study entry

Appendix C – Comorbidity Data Collection Forms:

- completed at the time of initial phase angle measurement -submitted within one week of completion

Appendix A - Eligibility and Source Document Checklists, Registration Form

CCCWFU # 99113

REGISTRATION GUIDELINES

The following guidelines have been developed in order to ensure timely registration of your patient.

All patients entered on any CCCWFU trial, whether treatment, companion, or cancer control trial, **must** be registered with the CCCWFU Protocol Registrar or entered into ORIS Screening Log within 24 hours of Informed Consent. Patients **must** be registered prior to the initiation of treatment.

In order to ensure prompt registration of your patient, please:

- 1. Complete the Eligibility Checklist (attached)
- 2. Complete the Protocol Registration Form (attached)
- 3. Alert the WFUHS registrar by phone, *and then* send the signed Informed Consent Form, Eligibility Checklist and Protocol Registration Form to the registrar, either by fax or e-mail.

Contact Information:

Protocol Registrar [contact] Protocol Registrar [contact]

Protocol Registrar E-MAIL ([contact])

*Protocol Registration is open from 8:30 AM - 4:00 PM, Monday-Friday.

4. Please fax/e-mail ALL eligibility source documents with registration. Patients **will not** be registered without all required supporting documents.

Note: If labs were performed at an outside institution, please provide a printout of the results. Please ensure that the most recent lab values are sent.

С	ccw	'FU # 9	99113 Eligibility Checklist	Page 1
Yes	No	N/A	Inclusion Criteria (All responses must be YES in order to enter study)	Eligibility Confirmation (registrar)
			 Is the patient hospitalized for newly diagnosed acute leukemia? 	
			Is the patient receiving induction treatment while hospitalized?	
			3. Is the patient willing and able to provide written informed consent?	
Yes	No	N/A	Exclusion Criteria (All responses must be NO in order to enter study)	
			1. Does the patient have a pacemaker or defibrillator?	
			2. Is the patient pregnant?	
			3. Does the patient have any abnormality which may, in the opinion of the investigator, compromise the safety of patients?	
			4. Is the patient unable or unwilling to follow protocol requirements?	

Signature: _____ Date: _____ Please send source documentation with Eligibility Form.

CCCWFU # 99113	Protocol Registration Form Pa	
DEMOGRAPHICS		
Patient: Last Name:	First Name:	
MRN:	DOB (mm/dd/yy):	//
SEX: □ Male □ Female Ethnicity (choose one): □ Hispa	anic □Non-Hispanic	
Race (choose all that apply): □ WHITE □BLACK □ AS	IAN	□ NATIVE AMERICAN
Height: inches	Weight:	lbs.(actual)
Zip Code:	-	
Primary Diagnosis:		
Date of Diagnosis: /	/	
PROTOCOL INFORMATION		
Date of Registration:	///	
MD Name (last) :		
Informed written consent (conse □ YES □ NO	ent must be signed prior to regis	stration):
Date Consent Signed:	///_	
PID # (to be assigned by ORIS)	:	

Protocol Registrar can be contact by calling [contact] between 8:30 AM and 4:00 PM, Monday – Friday. Completed Eligibility Checklist and Protocol Registration Form must be hand delivered, faxed or e-mailed to the registrar at [name] or [contact].

CCCWFU # 99113 Eligibility Source Documentation Checklist Page 3 (to be submitted with Protocol Registration Form) Source Documents Needed ✓ or N/A Documentation that patient is hospitalized for newly diagnosed acute 1 leukemia 2 Documentation that patient is receiving induction treatment while hospitalized 3 Signed informed consent document Documentation that patient is not pregnant 4 Documentation that patient is free from any condition or abnormality which 5 may, in the opinion of the investigator, compromise the safety of patients

Appendix B: Social and Medical History, Baseline Lab Data Collection Form (Page 1 of 2)

Demographics Social History:

Married:	Yes No _		
Tobacco use:	Current	Former	Never
Alcohol abuse:	Current	Former	Never

Baseline Labs on date of admission: (allow one decimal point)

WBC HEMOGLOBIN HEMATOCRIT	; ;	SODIUM POTASSIUM BUN GLUCOSE	; ;
PLATELETS NEUTROPHILS BANDs ANC		CREATININE ALBUMIN T. BILIRUBIN ALK PHOS AST	
LDH	·	ALT GFR	``

Appendix B: Demographics, Social and Medical History, Baseline Lab Data Collection Form (Page 2 of 2)

Past Medical History

Number of comorbidities: _____ (0-20)

Past History of:

(per documentation in medical record at time of admission)

Congestive Heart Failure	YN	Depression	YN
Coronary artery disease	YN	Osteoporosis	YN
Cerebrovascular Disease	YN	Rheumatologic disease (SLE, RA, scleroderma, S	
(Stroke, TIA) Diabetes Mellitus	YN	Cognitive Impairment	
COPD (Emphysema)	YN	VTE (Venous thrombosis, DVT	YN , PE)
Hypertension	YN	Cardiac valve disease	YN
Renal Dysfunction	YN	Cirrhosis	YN
	YN	MDS (H&P only)	YN
(Excludes non-melanoma	SKIN)	MDS (path report only)	Y N
If yes, then cancer type			
Prior treatment with: (check) Chemotherapy Radiation Surgery			

Appendix C: Comorbidity Data Collection Forms (Page 1 of 3)

Charlson Comorbidity Index

Comorbidity and score (circle)	
Myocardial infarction	1
Congestive heart failure	1
Cerebrovascular disease	1
Peptic ulcer	1
Hepatic ulcer (mild)	1
Diabetes (mild/moderate)	1
Pulmonary disease (mild/moderate)	1
Diabetes (with severe end stage organ damage)	2
Renal disease (moderate or severe)	2
Hepatic disease (moderate or severe)	3
Solid tumor with metastases	6

Total Score_____

Appendix C: Comorbidity Data Collection Forms (Page 2 of 3)

Hematopoletic Cell Transplant Comorbidity Index	
Comorbidity and score (circle)	
Cardiac (CAD, CHF, MI, EF ≤ 50%)	1
Arrhythmia (Atrial fibrillation or flutter, sick sinus or ventricular arrhythmia)	1
Cerebrovascular disease (TIA or CVA)	1
Peptic ulcer (Requiring treatment)	2
Hepatic Disease (mild) (Chronic hepatitis, bilirubin>ULN to 1.5 X the ULN,or AST/ALT>ULN to 2.5 X the ULN)	1
Diabetes (Requiring treatment with medication)	1
Pulmonary (moderate) (DLCO and/or FEVI 66-80% or dyspnea with slight activity)	2
Rheumatologic (SLE, RA, polymyositis, mixed CTD, or polymyalgia rheumatica)	2
Inflammatory bowel disease (Crohns disease or ulcerative colitis)	1
Renal (moderate/severe) (Serum creatinine>2mg/dL, mixed CTD, or prior renal transplant)	2
Prior solid tumor (Treated at any point in patient's history, excluding non-melanoma)	3

Appendix C: Comorbidity Data Collection Forms (Page 3 of 3)

Hepatic (moderate/severe) (Liver cirrhosis, bilirubin>1.5 X the ULN, or AST/ALT>2.5 X the ULN)	3
Obesity (Body mass index > 35 kg/m²)	1
Infection (Requiring use of antimicrobial treatment)	1
Psychiatric Disturbance (Depression or anxiety requiring psychiatric consult or treatment)	1
Heart Valve Disease (Except mitral valve prolapse)	3
Severe pulmonary (DLCO and or FEVI ≤ 65% or dyspnea at rest or requiring oxygen)	3
Total score:	

Appendix D – Phase Angle Measurement Form

To be completed with each phase angle measurement:

ORIS Assigned PID:			
Physical Exam:			
Date of Exam: / / /			
Weight: (kg)			
Height: (cm)			
Systolic Blood Pressure (SBP): (50-250)			
Diastolic Blood Pressure (DBP): (30-130)			
Pulse: (30-180)			
Phase Angle: R: Xc			

For AML Patients: Second Phase Angle Measurement taken just prior to the nadir marrow:

Physical Exam:

Date of Exam: ____ / ____ / ____ / ____ / ____

Weight: ____ (kg)

Height: _____ (cm)

Systolic Blood Pressure (SBP): _____ (50-250)

Diastolic Blood Pressure (DBP): _____ (30-130)

Pulse: _____ (30-180)

Phase Angle: _____ R:____ Xc_____

Appendix E – Bone Marrow Biopsy and Treatment Data Collection Forms

BONE MARROW BIOPSY:
DATE//
Diagnosis: AML or ALL Blast %:
CYTOGENETICS:(free text)
RISK GROUP: FAVORABLE INTERMEDIATE UNFAVORABLE
APL: YESNO Hypoplastic marrow cellularity %:
TREATMENT:
HOSPITALIZED FOR INDUCTION CHEMOTHERAPY: Y N
DATE OF ADMISSION:
DATE OF DISCHARGE:
DATE INDUCTION CHEMOTHERAPY INITIATED:
TYPE OF CHEMOTHERAPY ADMINISTERED (check one):
 AraC+anthracycline+etoposide (7+3+3) AraC+ anthracycline (7+3) As per CALGB 10102 other(document regimen)
NUMBER OF CYCLES OF CHEMOTHERAPY:(range 0-5)
RESIDUAL DISEASE ON 14-DAY BONE MARROW BIOPSY: Y N N/A
REQUIRED ICU DURING HOSPITAL STAY: Y N
DEATH WITHIN 30 DAYS OF INITIAL TREATMENT: Y N
DEATH WITHIN 60 DAYS OF INITIAL TREATMENT: Y N
DISPOSITION: HOME SNFALF HOSPICE DECEASED
Need for total parenteral nutrition or feeding tube placement during induction hospitalization:

Y____ N____

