
Bioimpedance phase angle is prognostic in multiple disease states. Phase angle is measured by bioimpedance and reflects cell membrane integrity, nutritional status and muscle mass¹⁶. It has been found to be prognostic in a number of conditions such as end stage renal disease, HIV and COPD¹⁷⁻¹⁹. Additionally, it is prognostic in multiple tumor types including pancreatic, colorectal, breast and head and neck. In a recent report it was found to be strongly prognostic for patients with hematologic malignancies undergoing allogeneic stem cell transplants²⁰. Standardized phase angle measurements are made non-invasively, can be done quickly and reproducibly and with no patient discomfort. Measurements are taken by placing 2

electrodes on the hand and 2 on the foot from the same side of the patient. A small voltage is applied between the electrodes and the timing of induced the current is measured. The current is approximately 1000 times lower than the sensitivity of sensory neurons and thus cannot be felt by the patient and has no known biological effect. This study seeks to establish the feasibility and prognostic power of standardized phase angle in acute leukemia patients undergoing intensive induction chemotherapy.

2.0 Objectives

2.1 To determine the feasibility of obtaining standardized phase angle measurements on patients hospitalized for treatment of newly diagnosed acute leukemia.

2.2 To evaluate the association between standardized phase angle measured at the start of therapy and treatment-related outcomes including: Primary outcome: Treatment related mortality (defined as 60-day mortality) Secondary outcomes: Evaluate the association of the day 14 standardized phase angle and treatment related outcomes, 30-day mortality, length of hospitalization, transfer to intensive care unit during induction, treatment response (14 day bone marrow response, complete remission), receipt of post-remission therapy, overall survival.

2.3 An exploratory analysis investigating associations with the primary and secondary outcomes using different ways to categorize the baseline standardized phase angle measurement (obtained on the first day of treatment) and, for AML patients, the standardized phase angle measure obtained just prior to the nadir marrow.

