5.0 Data Management

All data will be de-identified and stored in a password protected REDCap database in accordance with HIPAA. Research Electronic Data Capture (REDCap) software is a secure, web-based application designed to support survey creation, survey administration and data capture for research studies. Records to be kept on each subject will include only the data specified in Appendices B, C, D, E and F. Only study personnel will have access to the data.

6.0 Registration

Eligible patients must be registered with the CCCWFU Registrar. Following registration, patients should have a baseline phase angle measurement taken. If a patient does not agree to have the measurement following registration, the patient's registration on the study may be canceled. The Registrar should be notified of cancellations as soon as possible.

To register a patient, the following documents should be completed by the research nurse or data manager and faxed [contact]) to the Registrar:

- Signed patient consent form/HIPAA authorization form
- On-Study/Registration Form (Appendix A)

The research nurse or data manager will then call [contact]) the Registrar between the hours of 0800-1600 EST Monday-Friday to verify eligibility. To complete the registration process, the Registrar will:

- assign a patient study number
- register the patient on the study

7.0 Statistical Considerations

Description of measures

Standardized phase angle

Standardized phase angle will be calculated as in 20 (standardized phase angle = (measured phase angle–phase angle ref)/SD ref). Reference values and standard deviation come from measurements of phase angle in over 200,000 healthy German adults²¹.

Mortality

30 day mortality rate is defined as the percent of patients no longer alive at 30 days after registration. In the rare case that a patient is lost to follow up before 30 days, the patient will be treated as missing.

60 day mortality rate is defined as the percent of patients no longer alive at 60 days after registration. Patients that are discharged to hospice care before 60 days without a known date of death will be counted towards 60 day mortality. In the rare case that a patient is lost to follow up before 60 days, the patient will be treated as missing.

Treatment response

14 day bone marrow response is defined as hypoplastic marrow with less than 20% cellularity and 5% blasts.

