Complete remission is defined as less than 5% marrow blasts, absolute neutrophil count >1000, platelet count >100,000 and freedom from red cell transfusions.

Feasibility Analysis

If the study fails to accrue 20 patients during the first year of accrual it will be deemed unlikely to meet its ultimate accrual goal and the study will be terminated.

Primary analysis

This study's primary endpoint is the association between standardized phase angle and 60 day mortality. Standardized phase angle will be treated as a continuous measure for the primary analysis. Since we will be using a standardized measure of phase angle, for power calculations we will assume a standard deviation of one and investigate the effects of a one unit change. A sample size of 102 patients would give us 80% power to detect an odds ratio of 2.1, using a logistic regression model with a 0.05 significance level and a 60 day mortality rate of 20%. With an expected accrual rate of 50 patients per year, the study should complete accrual in approximately two years and complete follow-up (two year follow-up) four years after the first patient is enrolled. Descriptive statistics will be used for baseline characteristics. Important baseline characteristics, such as age, will be added to the regression model as covariates for additional analysis.

Secondary analysis

We will use logistic regression to analyze the association between standardized phase angle and the secondary outcomes of 30 day mortality, transfer to the intensive care unit, 14 day marrow response, complete remission and receipt of post-remission therapy. The association with overall survival will be evaluated using a Cox proportional hazards model. We will use a linear model to look at the association with length of hospital stay. It is likely that the length of hospital stay will not be normally distributed and will need a transformation to satisfy the normality assumption of the linear model. Feasibility will be analyzed qualitatively.

Exploratory analysis

We will explore other versions of the standardized phase angle measure and how they relate to the primary and secondary outcomes. We will evaluate using categorical cut points of the baseline measure and the standardized phase angle measure captured just prior to the nadir marrow (for AML patients).

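### The only ICU item collected is undated and covers the whole hospital stay, so ICU care before induction or before the baseline phase angle would be scored as an outcome of it

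*Combined protocol and SAP*

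**What the plan says.** Objective 2.2 sets out to relate "standardized phase angle measured at the start of therapy" to a list of outcomes. One of the secondary ones is "transfer to intensive care unit during induction".

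Section 7.0, under Secondary analysis, names "30 day mortality, transfer to the intensive care unit, 14 day marrow response, complete remission and receipt of post-remission therapy" as outcomes for logistic regression. It gives no time window for the ICU outcome. The Description of measures in the same section defines mortality and treatment response but not ICU transfer.

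Appendix E holds the only ICU item: "REQUIRED ICU DURING HOSPITAL STAY: Y N". The same form has separate fields for "DATE OF ADMISSION" and "DATE INDUCTION CHEMOTHERAPY INITIATED".

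Section 5.0 adds: "Records to be kept on each subject will include only the data specified in Appendices B, C, D, E and F". Section 4.0 allows the baseline reading at any time in the first three days of treatment. The criteria in Section 3.0 do not exclude patients who are or have been in an ICU.

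**The concern.** The objective and the form describe different events. The objective counts a transfer, and counts it during induction. The form counts any need for ICU care, over a stay that starts at admission. Three kinds of patient can be a Yes on the form although the event preceded the phase angle reading:

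- those admitted directly to an ICU;
- those whose ICU care ended before induction began;
- those who went to the ICU after chemotherapy started but before the baseline reading.

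The protocol wants a prognostic factor that is available early. An ICU stay that has already happened cannot be predicted by a later reading, and the illness behind it may itself have changed that reading. A regression on the form item would then estimate something other than the association named in Objective 2.2.

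**Working it through.** **1. The wordings side by side**

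| Place | Event | Window | Date of event |
|---|---|---|---|
| Objective 2.2 | transfer | induction | – |
| Section 7.0 | transfer | not stated | – |
| Appendix E | ICU required | hospital stay | none |

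**2. Can the data repair it?** The start of the stay, the start of induction and the date of the phase angle reading (Appendix D) are all recorded. The ICU date is not, and no other form, including the survival form in Appendix G, has an ICU item. Given Section 5.0, an analyst with a Yes cannot tell whether ICU care came before or after the reading.

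**3. How large could the effect be?** The documents give no ICU rate, effect size or power for this outcome, so there is no plan figure to reproduce. The inputs below are assumptions, except n = 102 and the OR of 2.1, which Section 7.0 gives for 60-day mortality.

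- x is minus the standardized phase angle, with SD 1, so an OR above 1 means lower phase angle goes with ICU care.
- A fraction p0 of patients had prior ICU care; their mean x is higher by Δ.
- Later ICU transfer follows logit(probability) = logit(0.20) + ln(OR)·x.
- The form records Yes for prior or later ICU care.

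*No true association (OR 1.0), Δ = 1.* The recorded rate is r = 1 − 0.80(1 − p0). The share of recorded events that are prior ICU care is f = p0/r. Recorded events then have mean x of fΔ and non-events a mean of 0. To a good approximation ln OR = fΔ / [1 + r·f(1 − f)Δ²], where the denominator is the pooled variance of x. For p0 = 5%: r = 0.240, f = 0.05/0.240 = 0.208, ln OR = 0.208/1.040 = 0.200, OR = 1.22.

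| p0 | r | f | OR, formula | OR, simulated | Rejection at 5% level, n = 102 (simulated) |
|---|---|---|---|---|---|
| 1% | 0.208 | 0.048 | 1.05 | 1.05 | about 5% |
| 2% | 0.216 | 0.093 | 1.10 | 1.09 | about 6–7% |
| 3% | 0.224 | 0.134 | 1.14 | 1.14 | about 8–9% |
| 5% | 0.240 | 0.208 | 1.22 | 1.22 | about 14–15% |
| 10% | 0.280 | 0.357 | 1.40 | 1.40 | about 32–34% |

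With Δ = 0.5 the simulated ORs at 3%, 5% and 10% are about 1.07, 1.11 and 1.19. With p0 = 0 the OR stays at 1.0.

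*True OR 2.1, simulated:*

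| Δ | p0 = 3% | 5% | 10% |
|---|---|---|---|
| 0 (prior ICU unrelated to phase angle) | about 1.95 | about 1.87 | 1.70 |
| 0.5 | 2.10 | about 2.07 | 2.06 |
| 1 | 2.22 | about 2.26 | 2.43 |

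A second set of assumptions gives the same picture. Take an induction ICU rate of 15% or 25%, a true OR of 2.1, and prior ICU care in 5% or 10% of patients. The recorded OR is 1.57–1.89 if prior ICU care is unrelated to phase angle. It is 2.39–2.84 if prior ICU care is strongly related to it (OR 4 per SD).

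In patients, 3% to 10% of 102 is about 3 to 10 people.

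**The case against.** **The wordings may be closer than they look.** The ICU item follows a question about hospitalization for induction, the nutrition item on the same form refers to the induction hospitalization, and Appendix F covers the time after it. *During induction* in Objective 2.2 could mean that same hospitalization. This largely stands: the stay is very probably the induction admission. It leaves open the days from admission to the baseline reading, and direct ICU admission as against transfer.

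**A form prompt is not an endpoint definition.** Objective 2.2 and Section 7.0 both say transfer, and the plan never states that the Appendix E item is the analysis variable. But it is the only ICU variable, and Section 5.0 leaves no other source.

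**Prior ICU care may be rare among those enrolled.** Patients must be able to consent (Section 3.1), the investigator may exclude on safety grounds (3.23), and Appendix A requires registration before treatment starts. These points do not exclude ICU patients, but they make high rates less likely. At 1–2% the effect is small, with rejection close to the nominal 5%.

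**The three-day window may be narrower in practice.** Objective 2.3 and Section 9.0 speak of a reading on the first day of treatment. Section 4.0 allows three days. ICU care before induction remains a problem under either.

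**A reader might infer that the OR must be biased away from 1.** The documents do not support that. The direction depends on how far phase angle differs in prior-ICU patients and on the true OR. At a true OR of 2.1 there is almost no bias with a 0.5 SD difference, and there is attenuation with none.

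**Conclusion.** The mismatch holds. As written, the plan would score ICU care that precedes the predictor as an outcome of it, and the retained data could not separate the two. The estimated OR would combine prior and later ICU care.

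The size is unknown. Under the assumptions above it runs from nothing (no prior ICU stays), through an OR of about 1.05–1.09 where the truth is 1.0 (1–2% prior ICU, 1 SD lower), to 1.14–1.40 (3–10%). In the other direction, a true OR of 2.1 falls to about 1.70–1.95 at 3–10% if prior ICU care is unrelated to phase angle. All of this rests on assumed ICU rates and shifts.

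A reader might also infer that the main secondary analysis in all 102 patients is compromised. The documents do not rank the secondary outcomes, and ICU transfer carries no power claim. The figure of 102 is the sample size for 60-day mortality, and that primary analysis does not use the ICU item. The point concerns one secondary outcome. It is worth correcting because the repair is cheap while records are being abstracted and the study database alone cannot supply it afterwards.

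**What to change.** Use one definition in Objective 2.2, Section 7.0 and Appendix E: transfer to ICU during the induction hospitalization, after the baseline phase angle measurement.

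Replace the Appendix E item with two:

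- *Transferred to ICU: Y/N, date of first transfer.* If the first transfer precedes the reading, also enter the date of the next one, if any.
- *In ICU at or before baseline measurement: Y/N*, with Yes split into still in ICU at the reading or left before it.

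The Appendix D date then fixes the order of events. In Section 7.0, state that ICU care before the measurement is not an event, and that patients in ICU at the measurement are left out of this one analysis because they are not at risk of a transfer. Report how many patients each rule affects.

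This narrows Objective 2.2 slightly: a transfer after induction starts but before the reading would count under the present objective and not under the new definition. Report those transfers separately.

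The cost is two form fields from the same hospital record, short wording changes, and slightly fewer ICU events, so a slightly wider interval for this outcome. Patient care does not change.
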